19.3. Enrollment Sample Size

The maximum sample size for primary safety and efficacy is that of primary safety or 140 subjects required at 30 days. Conservatively, correcting that number for approximately 12.5% attrition at 30 days requires enrollment of 160 subjects. With 160 subjects enrolled and accounting for 20% attrition by 1 year, it is expected that 128 subjects will be evaluable for primary efficacy at 1 year providing 96 to 99% power depending on the proportion enrolled in each disease state.

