Sample Size Rationale: With an expected FAS sample size of N=128, one-sided Type I error less than or equal to 2.5%, and assumed primary patency at 12 months equal to .96, .87, .79, i.e. the point estimates for primary patency from Razavi et al for nonthrombotic, acute thrombotic, and chronic postthrombotic respectively, the power for primary efficacy ranges from 96 – 99% depending on proportion in each disease-state given a minimum of at least 20% in each group. The table below provides the matrix of simulated power varying the ITT proportions for the disease states.

Power Calculations Using Simulation for the Primary Statistical Analysis

Proportion of Subjects Expected in Each Group			Assumed Freedom from Primary Efficacy				Calculated Performance Goal				Power at N=128 Evaluable (20% attrition for N=160 enrolled)
NT	AT	CPT	NT	AT	CPT	Pooled	NT	AT	CPT	PG	One-sided Type I error = 2.5%
0.3333	0.3333	0.3333	0.96	0.87	0.79	0.873	0.83	0.7	0.66	0.73	98%
0.2	0.2	0.6	0.96	0.87	0.79	0.84	0.83	0.7	0.66	0.702	96%
0.2	0.6	0.2	0.96	0.87	0.79	0.872	0.83	0.7	0.66	0.718	99%
0.6	0.2	0.2	0.96	0.87	0.79	0.908	0.83	0.7	0.66	0.77	96%
0.3	0.3	0.4	0.96	0.87	0.79	0.865	0.83	0.7	0.66	0.723	97%
0.3	0.4	0.3	0.96	0.87	0.79	0.873	0.83	0.7	0.66	0.727	99%
0.4	0.3	0.3	0.96	0.87	0.79	0.882	0.83	0.7	0.66	0.74	98%
0.4	0.4	0.2	0.96	0.87	0.79	0.89	0.83	0.7	0.66	0.744	99%
0.4	0.2	0.4	0.96	0.87	0.79	0.874	0.83	0.7	0.66	0.736	98%
0.2	0.4	0.4	0.96	0.87	0.79	0.856	0.83	0.7	0.66	0.71	98%

Primary Statistical Analysis: The primary statistical analysis will be conducted in the FAS subjects overall and in the SARS-CoV-2 negative subgroup. The primary statistical comparison will use a one-sample Z-test comparing the proportion of subjects with primary patency to the PG using a one-sided $\alpha = 0.025$ equivalent to a z-score of 1.96. The variation in the proportion will be estimated using the disease-specific performance goals themselves, i.e. under the null, rather than use the estimated patency rates, i.e. under the alternative.

The estimates that will be observed for primary patency in each disease etiology are noted as follows:

$\hat{p}_{p_pat_NT}$ = The primary patency observed in the NT subjects.
 $\hat{p}_{p_pat_AT}$ = The primary patency observed in the AT subjects.
 $\hat{p}_{p_pat_CPT}$ = The primary patency observed in the CPT subjects.

The percent of subjects in the FAS with each disease etiology are noted as follows:

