p_{NT_FAS} = The proportion of FAS subjects with NT disease etiology.
 p_{AT_FAS} = The proportion of FAS subjects with AT disease etiology.
 p_{CPT_FAS} = The proportion of FAS subjects with CPT disease etiology.

The number of subjects in the FAS set with each disease etiology are noted as follows:

n_{NT_FAS} = The number of FAS subjects with NT disease etiology.
 n_{AT_FAS} = The number of FAS subjects with AT disease etiology.
 n_{CPT_FAS} = The number of FAS subjects with CPT disease etiology.

The primary patency for the hypothesis test is calculated as:

$$p_{p_pat} = p_{NT_FAS} * \hat{p}_{p_pat_NT} + p_{AT_FAS} * \hat{p}_{p_pat_AT} + p_{CPT_FAS} * \hat{p}_{p_pat_CPT}$$

with the variance of primary patency calculated as follows:

$$\text{var}(p_{p_pat}) = ((p_{NT_FAS})^2 PG_{NT}(1 - PG_{NT}))/ n_{NT_FAS} + ((p_{AT_FAS})^2 PG_{AT}(1 - PG_{AT}))/ n_{AT_FAS} + ((p_{CPT_FAS})^2 PG_{CPT}(1 - PG_{CPT}))/ n_{CPT_FAS}$$

Such that the Z score is calculated as follows:

$$Z = (p_{p_pat} - PG) / \text{square root}(\text{var}(p_{p_pat}))$$

When $Z > 1.96$, the primary patency is found to be significantly greater than the performance goal with two-sided Type I error held at 5%, i.e. two-sided p-value < 0.05 .

The two-sided p-value in the SARS-CoV-2 negative subgroup and all subjects will be calculated and ordered from largest to smallest. If the largest p-value, is statistically significant at $p < 0.05$ then the

hypothesis test is statistically significant in both the SARS-CoV-2 negative subset and all subjects. If not, testing continues to the smallest p-value. If the smallest p-value < 0.025 then the hypothesis test is statistically significant in the group for which the smallest p-value is associated with. If the smallest p-value ≥ 0.025 , then the hypothesis test is not statistically significant in either the SARS-CoV-2 negative subset nor all subjects.

Additional Analysis: As a supportive analysis to the primary patency analysis, a Kaplan-Meier analysis will also be performed using the patency data overall and in the SARS-CoV-2 negative subset. Time 0 is the index procedure and the event is lack of patency based on 1) reintervention per definition 2) a non-patent stenosis assessment within the 12 month visit window. For subjects who do not experience an event, the time of censoring is the date of the last follow-up whether scheduled or unscheduled.

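### The supportive Kaplan-Meier patency curve is timed by last contact rather than by imaging, so its 12-month value can sit up to about 2.5 points high or well below the truth

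*Combined protocol and SAP*

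**What the plan says.** Section 19.11, under Additional Analysis, states: "As a supportive analysis to the primary patency analysis, a Kaplan-Meier analysis will also be performed using the patency data". This is done for all subjects and again for the SARS-CoV-2 negative subset. Time is counted from the day of the index procedure. The event rule reads: "the event is lack of patency based on 1) reintervention per definition 2) a non-patent stenosis assessment within the 12 month visit window". For everyone else, "the time of censoring is the date of the last follow-up whether scheduled or unscheduled". No sentence ties that follow-up to a stenosis assessment, and no read-out day or data cut is given for the curve.

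The primary proportion in the same section is built differently: its denominator holds only subjects whose 12-month status is known. It also allows a later patent assessment, with no earlier reintervention, to stand in for a missing 12-month one.

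Section 19.3 starts from 160 enrolled and takes off 20% for attrition: "it is expected that 128 subjects will be evaluable for primary efficacy at 1 year".

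**The concern.** Under the endpoint definition in Section 6.1, a subject fails through a clinically driven reintervention or through imaging. Without a reintervention, contact with the site says nothing about patency. A subject who is seen or contacted after the window, but has no evaluable 12-month scan, cannot have an imaging event yet still enlarges the risk set when others fail.

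The protocol leaves several routes to that position:

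- Unscheduled visits need duplex ultrasound only when clinically indicated (Section 15.6).
- Refusing the follow-up venogram or IVUS after a non-diagnostic duplex is not a deviation (Sections 8.1 and 15.3).
- Visits may be held by other means in a public health crisis (Section 15.7).
- Loss to follow-up is declared only after at least two consecutive missed visits and once the 12-month window has closed (Section 15.7).

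The event rule adds to this. A subject with no 12-month scan who is non-patent at 24 months, without reintervention, is event-free throughout the curve. The primary proportion would leave that subject out as unknown.

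At stake is what the curve can support. If it lies above the primary proportion only because unscanned subjects pad the risk set, it offers no independent confirmation.

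**Working it through.** **Inputs.** Enrolled 160, attrition 20% (Section 19.3). Section 19.11 gives "assumed primary patency at 12 months equal to .96, .87, .79" for nonthrombotic, acute thrombotic and chronic postthrombotic subjects. The 12-month window is ±30 days (Section 15.3), taken here as days 335 to 395.

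**The plan's figures reproduce.** 160 × 0.80 = 128 evaluable, leaving 160 − 128 = 32 without a 12-month result. With equal thirds, (0.96 + 0.87 + 0.79)/3 = 0.873 and the performance goal is (0.83 + 0.70 + 0.66)/3 = 0.73. The plan states no value for the Kaplan-Meier estimate itself.

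**Upward effect, closed form.** Let k subjects have no 12-month imaging but contact past the window. Put all failures at one time, found by imaging only. Expected failures are 128 × (1 − 0.873) = 16.256, and the curve reads 1 − 16.256/(128 + k).

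| k (assumed) | Curve | Excess over 0.873 |
|---|---|---|
| 0 | 0.873 | 0 |
| 8 | 1 − 16.256/136 = 0.881 | 0.8 point |
| 16 | 1 − 16.256/144 = 0.887 | 1.4 points |
| 32 | 1 − 16.256/160 = 0.898 | 2.5 points |

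Over the pooled values in the plan's power table, the k = 32 excess is 3.2 points at 0.84 (20.48/128 − 20.48/160) and 1.8 points at 0.908 (11.776/128 − 11.776/160).

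**Simulation with real dates.** Assumptions: scan days uniform over 335 to 395, failures found by imaging only, read at day 395. Each cell gives the values for 0 / 8 / 16 / 32 unscanned subjects still in contact.

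| Share with contact after the 12-month visit | Censor at last follow-up | Censor at last scan |
|---|---|---|
| All | 0.875 / 0.881 / 0.890 / 0.897 | 0.875 / 0.874 / 0.877 / 0.871 |
| Half | 0.827 / 0.838 / 0.852 / 0.864 | 0.827 / 0.828 / 0.834 / 0.830 |
| None | 0.559 / 0.574 / 0.594 / 0.637 | 0.559 / 0.558 / 0.557 / 0.570 |

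The first row agrees with the closed form within simulation error. The last-follow-up curve is never below the last-scan curve. If the unscanned subjects leave before the window, the two differ by 0 to 0.4 point.

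**Why the lower rows fall.** When follow-up ends on the scan day, patent subjects leave the risk set on the same days that failures are recorded, so late failures are divided by a shrinking number. With 128 distinct scan dates and nobody followed beyond them, the expected curve is the product of (1 − 0.127/j) for j = 1 to 128, which is about 0.49. Recording whole days creates ties and gives the 0.56 in the table. If half the failures come to light by reintervention, the k = 0 values are 0.853 (half) and 0.686 (none).

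**Read-out day.** Read at day 365 with everyone followed later and k = 0, both rules give 0.936, because failures imaged on days 366 to 395 are not yet counted.

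**Grouping by visit.** Treating the window as one interval and counting only subjects assessed in it returns 1 − 16.256/128 = 0.873, whatever the contact pattern afterwards.

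**The case against.** The case for leaving the plan alone has five parts.

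1. **Nothing is decided by this curve.** Success rests on the Z-test, which excludes subjects of unknown status. This stands.
2. **Missing data are covered elsewhere.** A reader might take the curve to be the only planned analysis that uses subjects without a 12-month scan. It is not: Section 19.7 requires best-case, worst-case and tipping-point analyses in the ITT sample, and the worst case counts every missing result as a failure. This stands.
3. **Imaging is required at every scheduled visit.** Section 8.1 asks for a repeat of non-diagnostic duplex scans, and Section 15.3 calls for venogram and IVUS at 12 months when duplex is inadequate. The 32 are the plan's attrition, so in the ordinary sense many would be gone before the window. This stands as a limit on size: 32 is an upper bound and zero is possible.
4. **The effect is small.** Even 2.5 points compares with a gap of 0.873 − 0.73 = 14.3 points between assumed patency and the performance goal. True of the upward effect, but not of the downward one.
5. **Counting non-patent scans at any visit would change the endpoint.** The endpoint requires IVUS confirmation, which Section 9.5 mandates among follow-up visits only at 12 months or with a reintervention, and conditionally at 24 and 36 months. This is a fair warning. It is met by counting only assessments that satisfy the endpoint definition.

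None of this makes last contact a valid end of follow-up for a failure that only imaging can show.

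**Conclusion.** A minor point that holds. The censoring rule is not tied to imaging, and it keeps unscanned subjects as event-free if they are still in contact past the window. Relative to imaging-based follow-up, this raises the estimate by 0 to about 2.5 points at pooled 0.873. The size rests on an assumed 0 to 32 such subjects and on the rest having later contact. If nobody has later contact, the two censoring rules differ by up to about 7 points, but both curves are then far too low.

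Two stronger readings are tempting. The first is that every subject without imaging is credited as patent. Those who exit before the window are simply censored. The second is that the curve is always too high. Its direction depends on the read-out day and the data cut, neither of which is stated. After month 12 the next scheduled visit is at month 24, so at an early data cut many subjects could have the 12-month visit as their last contact, and the curve would then read low.

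Neither censoring rule corrects for unscanned subjects who truly do worse. If their patency were 0.60 (an assumption), overall patency would be (128 × 0.873 + 32 × 0.60)/160 = 0.818. That question belongs to Section 19.7.

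**What to change.** Replace the raw-date Kaplan-Meier with an interval-censored or visit-grouped estimate, overall and in the SARS-CoV-2 negative subset, read at the close of the 12-month window. The text should say that:

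- follow-up for imaging failure ends at the last evaluable core-laboratory stenosis assessment;
- an imaging failure lies between the last patent and the first non-patent assessment that meets the endpoint definition, including any required IVUS confirmation;
- a qualifying reintervention is an event on its own date;
- non-patent assessments outside the window are handled by the same rule.

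Do not simply move the censoring date to the raw date of the last scan. Where the 12-month scan is the last one, that gives about 0.56 against a true 0.873.

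The cost is a few sentences in Section 19.11 and slightly more programming. No new data are needed, and the sample size and primary test do not change. The resulting curve may be slightly less favourable than one padded with unscanned subjects.

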20. REGULATORY AND ETHICAL OBLIGATIONS

As the study Sponsor, Vesper Medical is responsible for the overall conduct and quality of the study, including the assurance that the study complies with the regulations and guidance that apply to medical devices evaluated under an IDE and GCP guidance (FDA Regulations, ISO 14155, and ICH E6). Additionally, Vesper Medical will ensure that qualified monitors and designated personnel are monitoring the study and that the Informed Consent process is followed per each site's local and national requirements.

20.1. Institutional Review Board / Ethics Committee Approval

21 CFR Parts 50 & 56; ISO 14155

The PI at each participating site is responsible for securing IRB/EC approval for this study protocol and the informed consent documents. The IRB/EC for each specific institution must review and approve this study protocol, the specific informed consent form, and any written materials for subjects to be used at that site **prior** to enrollment of the first subject. The Sponsor **must** also review and approve the final informed consent documents prior to their use. The Sponsor must receive a copy of any IRB/EC correspondence as well as the final approval letter and the final approved informed consent form from each IRB/EC. The IRB/EC approval letter must be signed by the IRB/EC chair or designee, identify the IRB/EC name and address, the clinical trial protocol by name or number, and the date the approval was granted.

The PI is also responsible for initiating and obtaining continuing review of the clinical trial. Continuing IRB/EC review and approval should not exceed intervals over one year but may occur at more frequent intervals as required by site specific IRB/EC policies. The PI must also provide the Sponsor with all correspondence and documentation of continued IRB/EC approval of the clinical trial.

20.2. Informed Consent

All sites shall comply with 21 CFR 50, provisions of ICH GCP, local IRB/EC policy, and all applicable local regulations (i.e. ISO 14155 for OUS Sites) for obtaining informed consent. Written informed consent is to be obtained for all subjects prior to treatment as described in **Section 10.1**.

Informed consent templates will be provided by the Sponsor to all participating clinical sites. Changes to this template made by the site based upon IRB/EC requirements must be provided to the Sponsor for review and approval prior to being submitted to the IRB/EC for review and approval. Any revisions required by a site's IRB/EC should also be provided to the Sponsor for review and approval prior to being submitted to the IRB/EC for final review and approval.

20.3. Protocol Amendment and Emergency Deviations

Changes to the research conducted under this protocol will be implemented with a formal protocol amendment. Amendments to the protocol may be initiated by the Sponsor or at the request of an PI. In either case, changes to the protocol must be approved by the Sponsor and submitted to the applicable

regulatory agency as appropriate. A protocol amendment cannot be implemented at the site without first being signed and acknowledged by the Investigator and approved by the IRB/EC.

Emergency deviations or modifications may be initiated without prior Sponsor or IRB/EC approval only in cases when the deviation is necessary to eliminate an immediate potential hazard to a subject. Emergency deviations or modifications implemented to protect the life or physical well-being of a subject must be reported to the Sponsor and site-specific IRB/EC **within 5 business days of occurrence**.

20.4. **Subject Confidentiality**

Confidentiality of subjects will be maintained throughout the study. A unique identification code will be assigned to each subject enrolled into the study. Access to the subject's medical records will be limited to authorized personnel of the Sponsor, their designated monitors, clinical site study staff, and authorized regulatory authorities as required by the IRB/EC and/or local or national agencies. Any data that may be published in abstracts or scientific journals and/or presented at medical meetings will at most reference the unique subject code and will not reveal any subject's identity. The Sponsor and their representatives will make every reasonable effort to protect the confidentiality of the subjects participating in the study.

All U.S. clinical trial sites must comply with the provisions of the Health Insurance Portability and Accountability Act (HIPAA) and in accordance with all applicable federal, local and institutional requirements. All European Union (EU) sites must comply with the provisions of the General Data Protection Regulation (EU) 2016/679) and in accordance with all applicable federal, local and institutional requirements.

21. CLINICAL TRIAL CONDUCT

21.1. Principal Investigator and Site Qualification

21 CFR 812.43; ISO 14155

All PIs and investigational sites will be selected by Vesper Medical through the PI and site qualification process. All selected PIs will be responsible for complying with all study-related and regulatory requirements and will be ultimately responsible for overseeing the conduct of the study at their respective investigational sites, per the Investigator Agreement.

All selected PIs will have the required training and expertise in performing peripheral vascular interventional procedures in a clinical research setting. The investigational sites where the study procedures and assessments are to be performed must have the adequate volume of the target subject population, experienced staff, as well as the appropriate facilities and equipment to meet the requirements of the study protocol and the expected enrollment time frames.

All PIs and research staff must be willing to undergo all study and device-related training and participate, assist, and comply with monitoring, audits, and inspections initiated by either the Sponsor and/or regulatory authorities.

21.2. Principal Investigator and Site Training

Training of the PI and clinical trial staff is the responsibility of the Sponsor and/or their designee. PIs and study staff will undergo site initiation visit training on the use of the study device, the study protocol, eligibility criteria, and device accountability prior to participating in the study. Training will also include, but is not limited to, instructions on timely and accurate eCRF completion, safety reporting timelines, as well as procedures for acquiring study-related images and associated timelines for submission to appropriate core laboratories. All training of the PIs and research staff must be documented on the site training log before performing any study-related function(s).

21.3. Clinical Monitoring

21 CFR 812.46; ISO 14155

Vesper Medical will designate qualified clinical monitors and oversee the conduct of this study. The clinical monitors will evaluate compliance with the protocol, GCP (FDA Guidance, ISO 14155, and ICH E6), any specific recommendations made by the site's IRB/EC, and the signed Investigator and Study Agreements.

The clinical monitor will conduct periodic monitoring visits to verify that the eCRFs agree with the source documentation and other records, that the rights and well-being of the subjects are being protected, and that the trial is being conducted in accordance with the approved protocol/amendments and GCPs. At the discretion of the Sponsor, periodic monitoring visits may occur either in-person or remotely. Periodic phone contact will also be conducted to ensure that the protocol is being followed and to assist the site with queries or other issues that may arise.

For record verification purposes during site monitoring visits, the clinical monitor and/or authorized Sponsor representative will be provided access to hospital records, original laboratory data, and other records and data as it relates to the study and as agreed to with the PI prior to the initiation of the trial. The PI will also make available to the clinical monitor all regulatory documents, all completed eCRFs, informed consent documents, source documentation, and other relevant records for all enrolled subjects at the site. It is important that the PI and other relevant site personnel are available for consultation with the clinical monitors during the monitoring visits and that sufficient time is devoted at the site to the monitoring process.

If the Sponsor and/or their authorized representative become aware that a PI is not complying with the study protocol, the PI Agreement, the Declaration of Helsinki, GCPs, applicable privacy standards, or any condition of the study imposed by the IRB/EC, the Sponsor or their authorized representative may immediately secure compliance, discontinue further shipments of the study devices and/or seize unused devices on-site. An inability to secure compliance and/or to complete an investigation into the factors that are inhibiting compliance may result in the PIs termination from the study by the Sponsor.

Study close-out visits will be conducted after the final follow-up visit is completed at each site. Following the resolution of any outstanding data discrepancies and adverse events, the remaining study devices will be collected and returned to the Sponsor. A final study report will be generated and submitted to the PI and the appropriate study oversight authorities. Study document retention requirements will be reviewed with each site during the close-out visit.

21.4. **Device Accountability**

All study devices will be provided to the PI by the Sponsor after being tested, released, and shipped according to appropriate standards. The PI and/or designee is responsible for the secure storage of and controlled access to the study devices and accountability. The study device shall not be dispensed to any person who is not a consented study subject under this protocol.

21.5. **Investigator Reports**

21CFR Parts 50 & 56; ISO 14155:2011 Section 4

All PIs will be responsible for preparing and submitting the following complete, accurate, and timely reports:

To the Sponsor and the IRB/EC:

- Any unanticipated adverse device effect occurring during an investigation as soon as possible but no later than 2 business days after first learning of the effect.
- Assist Sponsor in generating progress reports on the investigation at regular intervals, but in no event less often than yearly. If there is a study monitor, a copy of the report will also be sent to the monitor.

- Any deviation from the investigational plan made to protect the life or physical well-being of a subject in an emergency, as soon as possible but no later than 5 working days after the emergency occurs. Except in emergency situations, a protocol deviation may require prior Sponsor approval. If the deviation may affect the scientific soundness of the plan or the rights, safety, or welfare of subjects, prior FDA and IRB/EC approvals are required.
- Any use of the device without obtaining informed consent must be reported within 5 working days after such use.
- Assist Sponsor in generating a final report within 3 months following termination or completion of the investigation or an individual PI's part of the investigation.
- Any further information requested by FDA or the IRB/EC about any aspect of the investigation.

To the Sponsor:

- Withdrawal of IRB/EC approval of the PI's part of an investigation. (Due within 5 working days of such action). If the PI's IRB/EC withdraws their approval to conduct this study for any reason, the PI must notify the Sponsor as soon as possible, but no later than five working days after the withdrawal of the approval.

In addition, the PI is responsible for the reporting of all safety and device events per the timelines specified in **Section 17** and **Section 18**.

21.6. **Data Collection and Management**

Standardized eCRFs will be used to collect complete and accurate records of the clinical data required by the study in accordance with GCP guidelines. The PI and/or study staff under his/her direction is responsible for accurately recording the clinical data for this study within five (5) business days after each visit.

Continuous review of the data will be performed by qualified data managers to ensure accuracy and consistency. Data review will persist until the data are clean and ready for approval and locking.

21.7. **Safety Monitoring**

21.7.1. **Data Safety Monitoring Board**

To meet the ethical responsibilities and standards for research subjects, an independent board of multi-disciplinary physicians and subject matter experts shall serve as the Data Safety and Monitoring Board (DSMB) for the study. In order to enhance objectivity and reduce the potential for bias, the DSMB shall be independent of the Sponsor as well as the investigational sites/ PIs.

The DSMB shall serve as an independent body conducting a review and oversight of all key safety events to monitor the rate of occurrence (both site reported and CEC adjudicated events) as part of their mission to protect the rights and safety of research subjects. The DSMB will define the types of events that may require real-time reporting and the format and frequency of interim data reviews for aggregate event rates. The DSMB will conduct systematic interim safety reviews at pre-specified intervals as outlined in the DSMB charter. The committee will be responsible for making any recommendations to the Sponsor it deems necessary to protect subjects enrolled in the trial.

At the close of each meeting, deliberation will occur and each DSMB member will vote in favor of continuation of the study as designed, or modification of the study to protect the welfare of subjects enrolled into the study. The result of this vote will be recorded in the meeting minutes.

The methodology for performing these responsibilities shall be developed and outlined in the DSMB Charter.

21.7.2. **Clinical Events Committee**

An independent CEC consisting of a team of clinical experts with experience in the conduct of clinical trials shall be formed to review clinical events reported by the PIs, or at the request of the Sponsor to determine if they meet the pre-specified endpoint definitions. The CEC may also be called upon to review relevant SAEs to assess the relationship to the study device and/or study procedure. The CEC's determination of whether a clinical event meets the study-defined endpoint will be considered the primary determination for the purpose of reporting study results with the exception of endpoints derived from core laboratory analysis.

Operational provisions shall be established to minimize potential bias (i.e., the physicians serving on the CEC shall be blinded to the clinical site to the extent possible during adverse event review and adjudication). The methodology for performing these responsibilities will be outlined in the CEC Charter. The CEC will define the minimum required information necessary to facilitate their review of an event. This may include information from original source documentation and imaging media.

21.8. **Medical Monitoring**

The Sponsor will be responsible for identifying a Medical Monitor who possesses the appropriate expertise and medical knowledge to oversee all adverse events reported during the study. All adverse event reports will be directed to the Sponsor as well as the Medical Monitor. The Medical Monitor will be responsible for first-line and timely review of all adverse events in order to identify the seriousness, severity, causality, and expectedness (anticipated vs. unanticipated) of the event to the study device and/or study procedure. The Medical Monitor will also have responsibilities including but not limited to:

- Reviewing all reported AEs for UADE potential and notifying the Sponsor of the need for regulatory reporting;
- Determining the need for additional information or supporting documentation from the site regarding an adverse event to facilitate complete assessment;

- Providing thorough review and assistance, as needed, for generating documents (i.e., subject event narratives) subject to CEC review and adjudication;
- Providing answers to the sites, IRBs/ECs, and/or Sponsor to questions requiring medical expertise that pertain to the protocol (i.e., subject eligibility) or any other medical aspect of the study;
- Identifying potential need for an amendment to the protocol;
- Providing a review of safety information included in regulatory reporting, as needed.

The Medical Monitor will review all adverse events throughout the duration of the study until study completion.

21.9. **Central Core Laboratories**

To ensure that the clinical data and images are analyzed in a controlled, non-biased manner and that the results are analyzed using a standardized process, all venograms, intravascular ultrasounds, duplex ultrasound studies and X-rays obtained during this study will be submitted to a respective central core laboratory for analysis. Any core laboratories used during the conduct of this study will be identified and selected by the Sponsor.

The core laboratories will be responsible for analyzing the venograms, intravascular ultrasounds, duplex ultrasounds, and X-ray images according to the study eligibility criteria, the study endpoints, and requirement measurements according to the study protocol. Feedback will be provided to the sites and Sponsor regarding the quality of the tracings and images.

21.10. **Record Retention**

The PI is responsible for maintaining the following accurate, complete, and current records relating to his/her participation in this investigational study:

- Correspondence with another PI, an IRB/EC, the Sponsor, a monitor, or FDA;
- Records of receipt, use, or disposition of a device that relate to:
 - The type and quantity of the device, dates of receipt, and batch numbers or code marks;
 - Names of all persons who received, used, or disposed of each device;
 - The number of units of the device returned to the Sponsor, repaired, or otherwise disposed of, and the reason(s) therefore.
- Records of each subject's case history and exposure to the device, including:
 - Documents evidencing informed consent and, for any use of a device without informed consent, any written concurrence of a licensed physician and a brief description of the circumstances justifying the failure to obtain informed consent;

- All relevant observations, including records concerning adverse device effects (whether anticipated or not), information and data on the condition of each subject upon entering and during the course of the investigation, including information about relevant previous medical history and the results of all diagnostic tests;
- A record of the exposure of each subject to the investigational device, including the date and time of each use, and any other therapy;
- The protocol, with documents showing the dates of and reasons for each deviation from the protocol; and
- Any other records that FDA requires to be maintained by regulation or by specific requirement for a category of investigations or a particular investigation.

In addition, all PIs and Sub-Is shall disclose to the Sponsor sufficient and accurate financial information to allow the Sponsor to submit certification or disclosure of financial interests under 21 CFR 54. All PI(s) and Sub-I(s) shall update the information if any relevant changes occur during the course of the investigation and for one year following completion of the study.

The Sponsor, core laboratories, and clinical sites will maintain the study records until two (2) years after the last marketing application and until there are no pending or contemplated marketing applications or at least two (2) years have elapsed since formal discontinuation of clinical development of the investigational product. These records may be retained for a longer period of time if required by applicable regulatory agencies or by the Sponsor. In such an instance, it is the responsibility of the Sponsor to inform the PI/institution as to when these documents no longer need to be retained. The Sponsor will notify each site regarding the regulatory requirements for record retention during the study close-out visit.

Per regulations in Germany § 10 (7) MPKPV, the record retention period for the study documents shall be at least ten (10) years after the end of the study. These records may be retained for a longer period of time if required by applicable regulatory agencies or by the Sponsor.

21.11. **Audits/Inspections**

In accordance with GCP requirements, the Sponsor and/or designee may request access to all study records, including source documents, for inspection and duplication at any time. In the event that a PI is contacted by an applicable regulatory body in relation to this study, the PI will notify the Sponsor as soon as possible.

The PI and/or designees must be available to respond to reasonable requests by the authorized Sponsor, Clinical Research Organization (CRO) and regulatory agency representatives during the monitoring and inspection process. The PI must provide the Sponsor with copies of all correspondence that may affect the review of the current study (i.e. inspection observations) or their qualification as a PI in clinical studies conducted by the Sponsor. The Sponsor will provide any needed assistance to the clinical site for regulatory audits.

